10.3 ANALYSIS PLAN

Details of the efficacy and safety analyses are provided below. A separate statistical analysis plan will document further details of the statistical methods to be employed, including any changes to planned analyses specified within this protocol. The analysis plan will be finalized prior to any unblinding of study data by the Sponsor. Unless otherwise specified, all statistical tests will be 2-sided at alpha level of 0.05. All statistical calculations will be completed using the latest version of SAS[®].

The Intent-to-Treat (ITT) population will be defined as all subjects randomized into the study and receive at least 1 dose of study drug; all ITT subjects will be counted in the group to which they were randomized, regardless of the study drug they were actually given. All efficacy analyses will be performed on this ITT population, unless otherwise specified. The Safety population will be defined as all subjects enrolled into the study who received at least 1 dose of study drug; all Safety population subjects will be counted in the group corresponding to the study drug actually received, regardless of randomized assignment. All safety analyses will be performed on this Safety population, unless otherwise specified.

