10.3.1 Primary Efficacy Endpoint

The primary efficacy endpoint is the change in 6MWD measured at peak exposure from Baseline to Week 16. This study hypothesizes that inhaled treprostinil will improve exercise capacity after 16 weeks of therapy as compared with placebo when administered to subjects

with PH associated with ILD including CPFE. Non-parametric analysis of covariance will be used to estimate the treatment effect. The magnitude of treatment effect will be estimated with the Hodges-Lehmann median difference between 2 treatment groups. For subjects who discontinue from the study early, the last observation carried forward method will be used to impute the 6MWD at Week 16.

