10.3.2 Secondary Efficacy Endpoints

The effect of inhaled treprostinil will be formally tested on the following 3 secondary efficacy endpoints:

- 1. Change in peak 6MWD from Baseline to Week 12
- 2. Change in plasma concentration of NT-proBNP from Baseline to Week 16
- 3. Change in trough 6MWD from Baseline to Week 15

The similar approach for the analysis of primary efficacy endpoint will be used. No adjustment for multiplicity is planned.

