# 8.1 COVARIATES

The primary efficacy analyses of change in 6MWD at Week 16 will be adjusted for Baseline 6MWD (as a continuous variable). For sensitivity analyses of the primary efficacy endpoints and the secondary/exploratory endpoints with continuous variables, the baseline measure will always be the covariate.

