# 10.1.1.2 Primary Efficacy Analysis

All 6MWT data will be listed for all subjects. For each scheduled assessment, this listing will include the date test was performed (or date test was intended to be performed if subject is unable to attempt the test), start time of the test, nominal time point, last treatment dose, hours from last treatment dose to 6MWT start, if walk was attempted, total distance walked (in meters), whether subject received oxygen during the test, amount of supplemental oxygen, and any circumstances that adversely affected the walk (if any) including reason for not

attempting test (if any). The trough 6MWT measure will also be indicated. In addition, a listing of 6MWD with imputed values will be included for both peak and trough 6MWD data.

For the primary efficacy analysis, the effect of inhaled treprostinil versus placebo on change in peak 6MWD at Week 16 will be evaluated via analysis of covariance (ANCOVA). Change from Baseline in peak 6MWD is the dependent variable, and treatment and Baseline 6MWD are covariates in this ANCOVA model. Least squares means and standard errors for each treatment group, the least squares mean difference and its standard error, as well as a 95% confidence interval for the treatment group difference and p-value for treatment group comparison will be calculated from the ANCOVA model. This methodology will be carried out as follows:

- 1. Walk distances obtained after study drug termination or unblinding will be excluded (as described in Section 8).
- 2. Imputation rules in Table 8-1 will be applied.
- 3. The LOCF algorithm will be applied.
- ANCOVA will be conducted based on the pseudo SAS code: proc glm; class Treatment; model DistC = Treatment Dist0; run;

where DistC is the change from Baseline in peak 6MWD at Week 16 and Dist0 is the baseline measure of the 6MWD.

If the ANCOVA assumptions are violated, the primary efficacy analysis will be based on non-parametric analysis of covariance within the framework of the extended Cochran-Mantel-Haenszel test (Koch 1990, Koch 1998, Stokes 2000). Specifically, a Cochran-Mantel-Haenszel mean score test will be used on the standardized mid-ranks (ie, overall rank divided by the number of ranks +1, or "modified ridit" scores) of the residuals from an ordinary least squares regression with change from Baseline in peak 6MWD at Week 16 as a linear function of distance walked at Baseline (as a continuous variable). This methodology will be carried out as follows:

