- 1. Walk distances obtained after study drug termination or unblinding will be excluded (as described in Section 8).
- 2. Imputation rules in Table 8-1 will be applied.
- 3. Calculate ranks. The pseudo SAS code is as follows:

proc rank nplus1 ties=mean out=ranks;

var DistC Dist0;

run;

where DistC is the change from Baseline in peak 6MWD at Week 16 and Dist0 is the baseline measure of the 6MWD.

4. Linear regression model will be fit using the rank values generated above. The pseudo SAS code is as follows:

proc reg data=ranks noprint;

model DistC=Dist0;

output out=residual r=resid;

run;

where DistC is the rank value of the change from Baseline in peak 6MWD at Week 16 and Dist0 is the rank value of the baseline measure of the 6MWD.

5. A mean score test, using the values of the residuals as scores, compares the treatment groups. Cochran-Mantel-Haenszel mean score statistic and p-value will be calculated, using the NOPRINT and CMH2 options in the TABLES statement of the FREQ procedure of SAS. The pseudo SAS code is as follows:

proc freq data=residual;

tables Treatment\*Resid / noprint cmh2;

run;

where Treatment indicates the randomized treatment group, and Resid represents the residuals obtained from the above linear regression models.

In addition to the p-value from the non-parametric method described above, the Wilcoxon

rank sum test and the Hodges-Lehmann estimate of median difference (as an estimate of

location shift between 2 treatment groups for the placebo-controlled treatment effect) will be

provided. The Wilcoxon rank sum test and the Hodges-Lehmann estimate can be obtained

through the following pseudo SAS code:

proc npar1 way hl Wilcoxon; class treatment; var DistC; run;

where DistC is the change from Baseline in peak 6MWD at Week 16.

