# **10.2 SECONDARY EFFICACY MEASURES**

Secondary efficacy endpoints include the following:

- Change in peak 6MWD from Baseline to Week 12
- Change in plasma concentration of NT-proBNP from Baseline to Week 16
- Change in trough 6MWD from Baseline to Week 15

As specified in Section 8.4 above, the hierarchical (fixed-sequence) testing procedure will be employed to control the overall alpha level at 0.05.

# 10.2.1 Change in Peak 6MWD at Week 12

The methodology for primary efficacy analysis of change in peak 6MWD at Week 16 will also be carried out for the Week 12 assessment, as described above in Section 10.1.1.2.

# 10.2.2 Change in NT-proBNP at Week 16

The efficacy endpoint of change in NT-proBNP assesses if inhaled treprostinil decreases the level of NT-proBNP at Week 16 over placebo in subjects with PH-ILD. The null and alternative hypotheses are:

$$H_0: \mu_1 = \mu_2$$
$$H_a: \mu_1 \neq \mu_2,$$

where  $\mu_1$  and  $\mu_2$  are the median change from Baseline to Week 16 in NT-proBNP of the inhaled treprostinil and placebo treatment groups, respectively.

The NT-proBNP values will be listed for all subjects, including the nominal time point, collection date/time, normal range and "High/Low" flag. The values and their respective changes from Baseline will be summarized for each assessment. The difference between treatment groups for the change from Baseline to Week 16 will be tested using the analysis of covariance with change from Baseline in NT-proBNP as the dependent variable, treatment as the fixed effect, and Baseline NT-proBNP as the covariate. The pseudo SAS code is as follows:

proc glm; class treatment; model BNP\_C=Treatment BNP\_B; run;

where BNP\_C is the change from Baseline to Week 16 in NT-proBNP and BNP\_B is the NT-proBNP at Baseline.

If assumptions (normality and equal variance) for the parametric test are violated, the nonparametric Wilcoxon rank-sum test will be used. For subjects who do not have NT-proBNP measurements at Week 16, the LOCF imputation will be used. The analyses will also be performed for the data without imputation for the missing measures.

As an exploratory analysis, the NT-proBNP at Week 8 will be analysed using the same method as the NT-proBNP at Week 16.

### 10.2.3 Change in Trough 6MWD at Week 15

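### SAP 10.2.2: the NT-proBNP fallback drops the baseline adjustment that the other three tests in the hierarchy keep, at an avoidable cost in power

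*SAP*

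**What the plan says.** **NT-proBNP (SAP 10.2.2).** The main model is ANCOVA on the raw change with baseline NT-proBNP as covariate. The fallback reads: "If assumptions (normality and equal variance) for the parametric test are violated, the nonparametric Wilcoxon rank-sum test will be used". Week 8 NT-proBNP follows the same method.

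**6MWD (SAP 10.1.1.2, carried over by 10.2.1 and 10.2.3).** If the ANCOVA assumptions fail, the p-value comes from a non-parametric ANCOVA that uses baseline 6MWD. The unadjusted test is supplementary: "In addition to the p-value from the non-parametric method described above, the Wilcoxon" rank sum test and the Hodges-Lehmann estimate are also provided.

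**Protocol.** Section 10.3.1 says of the primary endpoint: "Non-parametric analysis of covariance will be used to estimate the treatment effect". Section 10.3.2 says of the three secondary endpoints: "The similar approach for the analysis of primary efficacy endpoint will be used". Section 10.3 leaves further detail to the SAP, "including any changes to planned analyses specified within this protocol".

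**SAP 8.1.** The covariate rule ends: "the secondary/exploratory endpoints with continuous variables, the baseline measure will always be the covariate". The sentence opens by naming sensitivity analyses of the primary endpoint, so its reach is open to more than one reading.

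**SAP 8.4.** The order is peak 6MWD at Week 16, peak 6MWD at Week 12, NT-proBNP at Week 16, then trough 6MWD at Week 15. Each is tested only if the one before it is significant.

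**The concern.** NT-proBNP is the only one of the four hierarchical tests whose fallback discards the baseline value. The SAP gives no reason for treating it differently, although a baseline-adjusted rank test is already coded for the other three.

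Change from baseline is usually correlated with baseline. A rank test that ignores this carries variance that adjustment would remove. If the ANCOVA assumptions fail, NT-proBNP may then miss significance when an adjusted test would not, and the hierarchy stops before trough 6MWD. Trough results would still be tabulated, but without a formal test.

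**Working it through.** **1. The plan's own figure.** Only 6MWD has a design calculation (difference 30 m, SD 75 m, two-sided 0.05, 90% power).
- n per arm = 2 × (75/30)² × (1.960 + 1.282)² = 131.3, so 132; the SAP states 133.
- Power at 133 per arm = Φ(30 / (75 × √(2/133)) − 1.960) = 90.4% (90.1% with the noncentral t).
- 266 / 0.85 = 312.9; the SAP states 314, that is 157 per arm.

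The design figures reproduce. None concerns NT-proBNP, so everything below rests on assumed distributions.

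**2. Fallbacks side by side.**

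| Test in order | Main model | Fallback p-value | Baseline in fallback |
|---|---|---|---|
| Peak 6MWD, Week 16 | ANCOVA | non-parametric ANCOVA (10.1.1.2) | yes |
| Peak 6MWD, Week 12 | ANCOVA | same (10.2.1) | yes |
| NT-proBNP, Week 16 | ANCOVA | Wilcoxon rank-sum (10.2.2) | no |
| Trough 6MWD, Week 15 | ANCOVA | same as peak (10.2.3) | yes |

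**3. Analytic size.** Let r be the correlation between the rank of change and the rank of baseline. Adjustment multiplies the residual variance by 1 − r². If the adjusted test has 90% power, the unadjusted test has power Φ((1.960 + 1.282) × √(1 − r²) − 1.960), and the sample size needed without adjustment rises by 1/(1 − r²).

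| r (absolute) | Unadjusted power | Sample size ratio |
|---|---|---|
| 0.2 | 88.8% | 1.04 |
| 0.3 | 87.1% | 1.10 |
| 0.4 | 84.4% | 1.19 |
| 0.5 | 80.2% | 1.33 |

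**4. Simulated size.** Wilcoxon on raw change was compared with the rank ANCOVA as coded in SAP 10.1.1.2: rank change and baseline, regress one on the other, then a mean score test on the residuals. Each cell used 157 per arm and 10,000 trials. NT-proBNP was log-normal with log SD 0.8 to 1.3, baseline to Week 16 log correlation 0.6 to 0.9, and treatment ratio 0.70 to 0.80. Drift is a common log shift in both arms. There were 36 cells per drift. The example columns use log SD 1.0, correlation 0.8, ratio 0.80.

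| Drift | Wilcoxon's loss, points: median (range) | Example power, Wilcoxon / rank ANCOVA | Chance of stopping here (1 − power) |
|---|---|---|---|
| −0.2 | 10.1 (0 to 18.0) | 0.66 / 0.80 | 34% / 20% |
| 0 | 4.7 (0 to 11.3) | 0.75 / 0.81 | 25% / 19% |
| +0.2 | 1.7 (0 to 7.5) | 0.80 / 0.81 | 20% / 19% |
| +0.4 | 0.4 (0 to 3.7) | 0.83 / 0.83 | 17% / 17% |

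The stopping figures assume that both peak 6MWD tests have already succeeded and that the fallback is in use. At 133 per arm the example gives 0.59/0.73, 0.68/0.75, 0.74/0.76 and 0.77/0.77.

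**5. Other models.**
- Log change unrelated to baseline: loss at most 5.5, 1.1 and 0.2 points at drift −0.2, 0 and +0.2.
- Additive pg/mL effect unrelated to baseline: nil (−0.15 to +0.08 point).
- Additive effect with regression to the mean (error scale 150 to 200 pg/mL): about 2 points at a slope of change on baseline of −0.1, and 10 to 11 at −0.3.
- Over all 224 cells the coded rank ANCOVA was never more than 0.15 point below Wilcoxon, which is within simulation error.

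**6. Type I error.** The whole procedure was run in 12 null cells: Shapiro-Wilk or Brown-Forsythe at 0.05 triggering the fallback, otherwise ANCOVA. Type I error was 0.045 to 0.053 with the Wilcoxon fallback and 0.048 to 0.053 with the rank fallback.

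**7. Two versions in SAP 10.1.1.2.** The wording ranks the residuals of a regression on unranked values: "change from Baseline in peak 6MWD at Week 16 as a linear function of distance walked at Baseline". The code ranks first: "Linear regression model will be fit using the rank values generated above". The comparison is mixed. The worded version had 0.83 against 0.80 for the code in the example at drift −0.2, and 0.86 against 0.78 for an additive effect at slope −0.3. In one other model it lost 9 points to Wilcoxon (0.49 against 0.58).

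**The case against.** - **A reader might infer that the fallback breaches SAP 8.1.** The documents do not support that firmly. The sentence opens with sensitivity analyses and may be limited to them. Nor can it require every test to be adjusted, since SAP 10.1.1.2 itself adds an unadjusted Wilcoxon for 6MWD. On the broader reading it supports adjustment, and the main NT-proBNP model follows it, but that is support rather than proof.
- **A reader might infer a breach of the protocol.** Section 10.3.2 asks only for a similar approach, and 10.3 expects the SAP to record changes. The SAP departs from the protocol elsewhere too: parametric ANCOVA comes first for the primary endpoint, and a fixed sequence replaces no multiplicity adjustment. What stands is an unexplained inconsistency with SAP 10.1.1.2 and with the protocol's general approach.
- **Wilcoxon is valid and prespecified.** This stands. There is no type I error problem to report.
- **The largest losses need NT-proBNP to fall in both arms.** This stands. A log drift of −0.2 means a placebo fall of about 18% (1 − e^−0.2), and nothing in the documents supports it.
- **The simulations had no missing data, while SAP 8.3.2 applies LOCF.** As an extreme, setting 15% of changes to zero in the example gave Wilcoxon / rank ANCOVA 0.61/0.70, 0.69/0.73, 0.73/0.75 and 0.75/0.75 at the four drifts. The gap narrows to about 9 points at drift −0.2 and 4 at drift 0, but does not vanish.

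**Conclusion.** The point holds as a consistency and efficiency point. The NT-proBNP fallback alone drops baseline, and an adjusted alternative already stands in the same SAP.

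The size depends on the assumed distribution. With log-normal values and no drift the median loss is about 5 points (range 0 to 11). It grows if both arms fall, and shrinks to about nil with enough upward drift or with an additive effect unrelated to baseline. Nothing changes if the ANCOVA assumptions hold. The knock-on to trough 6MWD arises only when both peak 6MWD tests have succeeded. The case for change is the asymmetry: the gain runs from nil to substantial, and no model tried showed a material loss for the coded rank ANCOVA.

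A reader might also infer that the coded version is the more powerful of the two in SAP 10.1.1.2. The runs do not show that: the worded version is often as powerful or more so.

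**What to change.** Before unblinding, replace the fallback sentence in SAP 10.2.2. If the ANCOVA assumptions fail, take the p-value from the baseline-adjusted non-parametric ANCOVA of SAP 10.1.1.2, using change in NT-proBNP and baseline NT-proBNP. Keep the Wilcoxon test and the Hodges-Lehmann estimate as supportive. Week 8 then follows automatically.

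Name one version of the procedure, since wording and code differ. The coded version (steps 3 to 5) is a safe default because it did not materially lose to Wilcoxon in any model tried. The worded version would also be defensible if fixed in advance.

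The SAP gives no diagnostic or threshold for calling the assumptions violated. That gap also affects 6MWD and is a separate point, but a rule could be set in the same edit.

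**Cost.** One or two sentences reusing existing code, with no new data, endpoint or table. **Downside.** The rank ANCOVA yields only a p-value. The reported Hodges-Lehmann estimate stays unadjusted and may disagree with that p-value near 0.05, as the SAP already accepts for 6MWD.

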### **10.3 EXPLORATORY EFFICACY MEASURES**

Exploratory efficacy endpoints include the following parameters:

- Change in peak 6MWD from Baseline to Week 4
- Change in peak 6MWD from Baseline to Week 8
- Change in quality of life as measured by SGRQ from Baseline to Week 16
- Time to clinical worsening will be evaluated as an exploratory endpoint from the time to randomization until 1 of the following criteria are met:
  - a. Hospitalization due to a cardiopulmonary indication
  - b. Decrease in 6MWD >15% from Baseline directly related to disease under study, at 2 consecutive visits and at least 24 hours apart
  - c. Death (all causes)
  - d. Lung transplantation
- Change in DSP from Baseline to Week 16

# 10.3.1 Change in Peak 6MWD at Weeks 4 and 8

The methodology for primary efficacy analysis of change in peak 6MWD described in Section 10.1.1.2 will also be carried out for the assessments obtained at Week 4 and Week 8.

# 10.3.2 Change in SGRQ at Week 16

The responses to the SGRQ questionnaire at Baseline and Week 16 will be converted to the Total score and 3 domain scores according to the SGRQ manual (Jones 2002). Scores for Total and each domain will range from 0 to 100, with higher scores indicating more limitations. Both individual item responses as well as calculated scores will be listed. The change from Baseline for the Total and 3 domain scores (Symptoms, Activity, and Impacts) will be calculated.

The Total score and for the 3 domain scores as well as their changes from Baseline will be summarized by treatment group using descriptive statistics.

For the Total score and each of the 3 domain scores, treatment differences (inhaled treprostinil vs. placebo) will be tested by using analysis of covariance with change from Baseline as the dependent variable, treatment as a fixed effect, and baseline score as the covariate. The analyses will be based on the observed data with no imputation.

The pseudo SAS code is as follows:

proc glm; class treatment; model Score\_C=Treatment Score\_B; run;

where Score\_C is the change from Baseline in Total score or each of the 3 domain scores and Score\_B is the corresponding score at Baseline.

#### 10.3.3 Time to Clinical Worsening

• Data on the clinical worsening assessment page of the eCRF will be used to determine clinical worsening status. Investigator-reported clinical worsening events including the date (study day) of the event, category of the clinical worsening event, Baseline 6MWD, first 6MWT details, and second 6MWT details will be listed. The time to clinical worsening will be calculated according to the rules described in Table 8-3 in Section 8.5.

The number and percentage of subjects with any clinical worsening and with each category of clinical worsening will be summarized by treatment group. Time to clinical worsening will be summarized by treatment group using product-limit estimates calculated by the Kaplan-Meier method and displayed graphically as Kaplan-Meier curves. A tabular summary of this analysis will include the number of subjects at risk (sample size), estimated median duration, and a 95% confidence interval for the median duration for each treatment group. The log-rank test, adjusted for Baseline 6MWD category, will be used to calculate the p-value for treatment differences in the ITT population.

The SAS Procedure LIFETEST will be used. The pseudo SAS statements are listed below:

proc lifetest; time TimeToWorsening\*Censor\_Status(1); strata B\_6MWD / group = Treatment test=all; run;

where B\_6MWD denotes the categorical Baseline 6MWD variable ( $\leq$ 350 meters versus >350 meters).

In addition, the Cox proportional hazards model will be fit to obtain the hazard ratio and its associated 95% confidence interval. The model will include treatment and Baseline 6MWD as explanatory variables. The SAS procedure PHREG will be used. The pseudo SAS statements are listed below:

where Dist0 denotes the Baseline 6MWD variable (continuous). If it is determined that the proportional hazards assumption does not hold for Baseline 6MWD, a stratified analysis will be conducted. The above SAS code will be amended to remove Dist0 from the model statement and add the 'strata B\_6MWD;' statement.

If the proportional hazards assumption does not hold for the Cox model, the restricted mean survival time (RMST) and its associated standard error will be calculated for each treatment group at Week 16 (Royston 2013). A 95% confidence interval will be constructed for the difference in RMST between the 2 treatment groups at Week 16.

# 10.3.4 Change in DSP

The DSP will be calculated, and DSP results will be included in the data listing for pulse oximetry. DSP values and their respective changes from Baseline to Week 16 will be summarized by treatment group. The difference between treatment groups for the change from Baseline to Week 16 will be tested using analysis of covariance with change from Baseline in DSP as the dependent variable, treatment as a fixed effect, and Baseline DSP measure as the covariate. The analyses will be based on the observed data with no imputation.

The pseudo SAS code is as follows:

proc glm; class treatment; model DSP\_C=Treatment DSP\_B; run;

where DSP\_C is the change from Baseline to Week 16 in DSP (m%) and DSP\_B is DSP at Baseline.

In addition, the DSP at Week 4, Week 8, and Week 12 will each be analyzed in the same way as the DSP at Week 16.

